Provided inclusion criteria are met, referrals will be scheduled for a telephone follow-up and scheduling for the first study. Individuals meeting eligibility criteria will be then be invited to the Coral Gables campus for an in-person COVID-19 and urine toxicology screening, prior to enrollment.

This study will actively recruit participants through the Community Outreach Core and Clinic Registry Project for the Center for HIV and research in Mental Health (CHARM) (IRB#20160911) of the University of Miami Center for AIDS Research. This mechanism allows IRB-approved study investigators the ability to search and identify potential willing research participants who meet study criteria. Upon contact, patients will verify their identity before being informed about the study and moving forward with the screening process. Patients will also be informed they have the right to change their consent in order to decline to be contacted for future studies.

Participants will also be recruited from the Miami MWCCS E-Prost Protocol No. 20210476, a study of men and women living with HIV in the US. The MWCCS has approved a concept sheet to refer MWCCS participants to this study. MWCCS participants who meet inclusion criteria will be asked by the MWCCS team, for willingness to participate in this study. Those interested participants will be given the contact information to contact the study directly, or if they prefer, their contact will be shared with study staff to contact them and provide information about the study.

Exclusion criteria. Following initial referral, participants will be assessed for PTSD over the phone through the primary care PTSD screen for DSM-5 (PC-PTSD-5) (64). After the participant has consented an in-house screener will also be used to assess substance dependency, suicidal ideation, history or treatment for schizophrenia or bipolar disorder, as well as severe dementia indexed by the Mini-Mental State Examination (MMSE) (65). Additional exclusion criteria include the following: 1) Left-handedness or ambidextrous; 2) Inability to tolerate the scanning procedures (e.g., claustrophobia); 3) Metal in body or prior history working with metal fragments (e.g., as a machinist); 4) Any other contraindications for MRI examination (e.g., metallic implants such as pacemakers, surgical aneurysm clips, or

IRB Study Number: 20190760

Version: 10 Date: 06/06/2022

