Randomized control trial with participants randomized to either the augmented trauma-writing intervention in English, the augmented trauma-writing intervention in Spanish or the daily-event-writing control in English/Spanish. Both experimental and control participants will visit the study on four occasions during a 4-week period so that they could write for 30 min in a private office.

8) Procedures

General overview. Upon meeting all eligibility criteria individuals will be consented into the study. Full participation in the study will involve 6 separate session. The first

IRB Study Number: 20190760

Version: 10 Date: 06/06/2022

and sixth sessions will last approximately 4-5 hours. On the evening prior to these sessions participants will perform an overnight fast and told to avoid drugs, alcohol and exercise. On the mornings of session 1 and 6 participants will report to the Cox Neuroscience Annex (CNA). Participants will be compensated \$80 each for the pre- and post-intervention sessions. Participants will also receive \$20 for attending each online writing session. Each participant will be compensated using the Zelle™ mobile banking application.

Screening. Prior to informed consent individuals will undergo screening using the 5-item PTSD checklist (PC-PTSD-5) in order to determine their eligibility to participate in the study. This is required given trauma interventions can potentially have adverse effects on asymptomatic individuals. . After the initial screening, referrals will be instructed to bring a copy of their most recent HIV labs (drawn within the last 6 months) for their in-person screening session, if they are HIV+. Labs will not be requested for the HIV- participants. After obtaining informed consent, we will make a copy of those labs, remove any identifiable information, and return the original copy to the research participant.

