Pre- and post-intervention Sessions 1a and 6a (intake). After adhering to overnight fasting protocols on both days participants will report to the Neuroimaging Suite (NIS) located on the second floor of the University of Miami Neuroscience Building (Cox Neuroscience Annex (CNA)) at [name]. Participants will be asked to wear comfortable clothing. Participants will undergo a series of screenings prior to being admitted entry into the NIS, including an fMRI metal screening and (see CNA standard operating procedures). After completion of the ICF the initial procedures will involve a clinical intake wherein participants will have their height, weight, waist and hip girth measured along with a standard information regarding medical history and pre-scan mood state, They will then have their time point 1 bloods drawn through an intravenous (IV) Teflon-based catheter inserted antecubital by an experienced phlebotomist. Three 10-15ml vials will be drawn in (2) heparin and (1) EDTA containers of blood will be drawn from all participants at time point 1.

Pre- and post-intervention Sessions 1b and 6b (MRI). Following the blood draw, the participant will have a 10-minute mock scan to allow the them to become acclimated to the MR environment and the cognitive task. Following the mock scan participants will need to complete an fMRI metal screening and be interviewed by the MR tech to ensure there are no potential hazards during scanning. Prior to the scan, and after the scan participants will be asked to provide a saliva sample. We will collect a small amount of saliva, using a disposable salivette to measure stress hormones and inflammation. During the scan, simultaneous recording of pulse, respiratory rate, and blood pressure will take place to monitor physiological arousal levels. Immediately, following the scan, the IV line will be flushed. At the conclusion of the real MRI session (time point 2) an additional (2) 20ml vials of blood will be drawn in heparinized tubes.

IRB Study Number: 20190760

Version: 10 Date: 06/06/2022

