Pre- and post-intervention Sessions 1b and 6b (post-scan assessments). Following the blood draw (T2), participants will be escorted to a separate room. Within this room, they will be fitted with electrodes for measurement of heart rate, respiratory rate and blood pressure during the completion of a behavioral self-compassion task. This task will take approximately 30 minutes to complete. Following completion of this task a third blood draw (T3) will be performed and (2) 20ml tubes will be collected for immediate processing. Following the compassion task a battery of psychosocial and neurocognitive measures will be administered lasting approximately 90 – 120 minutes. The estimated time of completion for all Session 1a & 6a activities is 4 hours per session. Participants will complete a psychosocial battery of self-report questionnaires using a laptop or personal computer (See Table 1). Following the surveys participants will engage in an exit interview.

Sessions 2-5: Arms and Interventions.

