Trauma Recall in fMRI. The 5 minutes allocated to trauma recall within the scanner will be facilitated by an “autobiographical script-driven imagery” protocol adapted for the fMRI environment (89, 90). During the protocol participants will listen to recordings of personal trauma episodes (recorded during session 1a) and will be asked to focus on the evoked mental images and feelings. Recordings and prompts to recall the trauma in primary (Spanish) or secondary (English) language will be matched to the intervention group to which the participant was randomized. During the protocol four 40-second scripts will be constructed for each subject from personal interviews, describing either aversive (e.g., sexual or childhood trauma) or neutral events. Two traumatic and two neutral conditions will be selected and played during scanning counter-balancing for valence. Participants will be instructed to focus on scripts and maintain the evoked images and states. Participants will also rate their evoked emotional states after each scan using a modified version of the Positive and Negative Affect Schedule (PANAS) (91). "Participants will be scanned at baseline and after the 4 WED sessions writing about trauma in English or Spanish or the 4 sessions of writing about daily activities (for the control group). Three salivary cortisol samples will be collected. The first sample will be collected just prior to beginning the 30-minute scan. The second and third collections being 5 minutes and 10 minutes after conclusion of the scan. Salivary ACTH will be assayed using a radioimmunoassay kit and analyzed at the DRI.

[figure not shown]

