Each encoding block is followed by a distracter epoch (19.5 s), where participants attend to a series of letters (i.e., “XXXXX—YYYYY”) to mimic the active stimulus. This is included to discourage rehearsal. Participants pressed with their right index finger when they saw the letters to control for motor activity in the other conditions. Immediately after each distracter epoch was a 19.5 s recall epoch, during which participants saw the first word of each pair from the encoding epoch that preceded it (e.g., UP - ___), attempted to recall the second word silently (3 s), and viewed a black screen (0.9 s). Subjects indicate perceived success at recalling the second word with a right index finger response and perceived failure with a left index finger response. After each recall epoch, participants focused on a crosshair (6 s) to allow for brain activity to return to its baseline. The sequence of encoding epoch, distractor epoch, and recall epoch repeated ten times. Before each new epoch began, there was a 3 s prompt to inform the participant which task they would need to perform. The full presentation of the task will last 12 m and 24 s.

The following neuropsychological tests and surveys will be administered during session 1 and 2. All forms are submitted and approved by IRB. Each assessment takes between 5 and 15 minutes to complete.

IRB Study Number: 20190760

Version: 10 Date: 06/06/2022

Table 1. Schedule of Assessments

Domain	Measure	T0 screen	T1 pre	T2 write	T3 write	T4 write	T5 write	T6 post
Cognitive	Mini-mental State Exam screener		X					
Psychiatric	Mini-International Neuropsychiatric Interview		X					
	Treatment Outcome PTSD Scale (TOP-8)		X					X
	PTSD Checklist for DSM-5 (PCL-5)		X					
	Civilian Spanish-English version PCL-C		X					
Acculturation	Brief Acculturation Scale For Hispanics (BASH)		X					
	Bidimensional Acculturation Scale (BAS)		X					
Psychosocial	Subjective Unit of Distress		X	X	X	X	X	X
	Impact of events scale—revised		X					X
	Spielberger State-Trait Anxiety Scales		X					X
	Anxiety Sensitivity Index		X					X
	Beck Depression Inventory		X					X
	Toronto Alexithymia Scale		X					X
	Multidimensional Interoceptive Awareness Scale		X					X
	Dissociative Experiences Scale		X					X
	Early Trauma Inventory		X					X
	Perceived Support Network Inventory		X					X
	Brief COPE		X					X
	*Brief Symptoms Inventory		X					X

IRB Study Number: 20190760

Version: 10 Date: 06/06/2022

	*Center Epi- Studies Depression Scale		X					X

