[name], M.D., Ph.D., will supervise and oversee of all mental health aspects of the study pertaining to treatment. [name] has over 20 years of experience in trauma assessment and counseling. To ensure protection of the participant procedures will be adopted from the mentor's initial study on WED in trauma survivors. Participants will answer a few survey items that let us know how they are doing both before and after the writing (or trauma recall sessions). These include the POMS (Profile of Mood States, short form), a SUDS (subjective unit of distress) question, and a question about "How upset are you about the topic you wrote/spoke about today? A fluent Spanish-English bilingual trauma therapist will be designated for monitoring these responses and will do a brief check-in (about 2 minutes) with each participant, paying particular attention to those whose scores indicate distress for the safety check. [name] has followed this protocol in trials using trauma writing and very few people (less than 5%) need extra counseling time. It should be noted that compared to 12-week cognitive behavioral therapy interventions, short expressive writing interventions such as the one proposed are shown to be non-inferior in terms of reducing post-traumatic stress (Sloan, Marx, Lee and Resick, 2018). As we have previously mentioned we will screen for such psychiatric comorbidity that would be deemed of risk to the participant's safety following traumatic recall, i.e., (a) exclusion for substance dependency as recall may exacerbate symptoms, (b) exclusion for recent or current suicidal ideation, and (c) current treatment of major depression and other neuropsychiatric conditions involving mood disturbance. To protect the participant's privacy all written samples will be de-identified. Furthermore, during the fMRI task there will be no oral or written record of the experience so as to preserve the participants right to confidentiality. The participant will be reminded that participation is voluntary, and they have the choice to participate or to withdraw from the study at any point.

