Upon arrival at the University of Miami Downton and Coral Gables locations there will be no additional costs for which the participants will be responsible. In addition, participants will be offered water and light snacks throughout the two sessions.

29) Consent Process

This study will follow the UM standard operating procedure for the Informed Consent Process for Research (HRP-090). The consent process will take place on the 7th floor of the BMRC located at the Clinical Research Building in downtown Miami. The research coordinator will describe the study to the participants and will go over the consent forms to make sure there are no additional questions that were not answered. Participants will be asked to sign one copy of the consent form and be provided with a signed copy. This consent form will cover participation at during both sessions 1 and 2. Approximately 20 – 30 minutes will be devoted towards going over the consent and an unlimited time will be provided for questions and answers prior to signing the consent. Participants will also be informed that they are able to refer to primary care physicians and/or loved ones before providing consent to participate in the study. In addition, study referrals will be verbally consented in order to complete the pre-screening process using

Cognitively Impaired Adults

Prior to participation in session 1 of the study, at the pre-screening, our group will administer the Montreal Cognitive Assessment or Mini-Mental State Exam. Individuals scoring at levels indicative of gross cognitive dysfunction or dementia will be excluded from the study. Each assessment takes approximately 5 minutes to administer.

30) Process to Document Consent in Writing

Standard operating procedures will be followed in order to attain written documentation of consent in conjunction with (HRP-091).

31) Drugs or Devices

None

IRB Study Number: 20190760
Version: 10 Date: 06/06/2022

References

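### At Session 6 neither suicide-risk instrument named in section 14 is scheduled before the second scripted trauma recall: the BDI-II item follows the scan and the MINI is given only at T1

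*Combined protocol and SAP*

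**What the plan says.** Section 15 (Provisions to Protect Subjects) states that "we will screen for such psychiatric comorbidity that would be deemed of risk to the participant's safety following traumatic recall", and lists recent or current suicidal ideation as an exclusion.

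The exposure is described in section 10 (Trauma Recall in fMRI). In the scanner, women "listen to recordings of personal trauma episodes (recorded during session 1a"). The scan takes place at baseline and again after the writing sessions, and the control arm is included.

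The screening text is spread over several sections:

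- Section 6 (Exclusion criteria): "After the participant has consented an in-house screener will also be used to assess substance dependency, suicidal ideation", together with other conditions and the MMSE.
- Section 8 (General overview): "Upon meeting all eligibility criteria individuals will be consented into the study".
- Section 8 (Sessions 1a and 6a, intake): "After completion of the ICF the initial procedures will involve a clinical intake". It covers body measurements, medical history and pre-scan mood, followed by a blood draw. No suicide-risk question is listed.
- Section 29 (Consent Process): "Prior to participation in session 1 of the study, at the pre-screening, our group will administer the Montreal Cognitive Assessment or Mini-Mental State Exam".
- Section 14 (Adverse Event): MINI data are reviewed for moderate to high suicide risk, and a BDI-II item may be used for high risk.
- Table 1: the row "Mini-International Neuropsychiatric Interview" is marked at T1 only. The Beck Depression Inventory, in the psychosocial group, is marked at T1 and T6.
- Section 8 (Sessions 1b and 6b, post-scan assessments): "Following the compassion task a battery of psychosocial and neurocognitive measures will be administered".

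**The concern.** A question about suicide risk can protect a woman from harm caused by recall only if it is asked and scored before the recall. Section 17 rates the research as above minimal risk because of the recall of severe trauma, and entry requires elevated PTSD symptoms.

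By Session 6 a woman may have written about her worst experience four times and then gone a further month before hearing her own trauma scripts again. If ideation has developed in that time, the schedule as written would ask about it only once the recall is over. The suicide-risk steps in section 14 start when ideation is disclosed or an item is endorsed, so their timing depends on when the question is put. This is a matter of participant safety and trial conduct, not of bias.

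**Working it through.** The plan gives no figure on this point to reproduce. The check is one of order, with a little arithmetic.

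**Step 1. Order within Sessions 1 and 6 (section 8).** Intake and first blood draw; mock scan; MRI, with trauma recall listed last of its four parts (section 10, Neuroimaging Protocol); second blood draw; self-compassion task of about 30 minutes; third blood draw; psychosocial and neurocognitive battery of about 90 to 120 minutes. The section heading covers both sessions.

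**Step 2. Where each instrument falls.**

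| Instrument | Before the Session 1 recall? | Before the Session 6 recall? |
|---|---|---|
| In-house ideation screener (section 6) | Probably; order not stated | Not scheduled again |
| MINI (section 14, Table 1) | At T1; place in the session not stated | Not scheduled at T6 |
| BDI-II suicide item (section 14, Table 1) | No; post-scan battery | No; post-scan battery |
| SUDS and POMS (section 14, Table 1) | Asked before, but measure distress | Asked before, but measure distress |

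The in-house screener is rated as probably first because section 6 groups it with the MMSE, and section 29 puts the MMSE before Session 1. Of the two instruments that section 14 names, 0 of 2 are scheduled before the Session 6 scan.

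**Step 3. Delay from scan to BDI-II item.** Earliest: 30 + 0 = 30 minutes. Latest: 30 + 120 = 150 minutes. Blood draws are not counted, and the item is assumed to fall anywhere in the battery.

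**Step 4. Age of the MINI result at Session 6.** Section 9 gives a 4-week writing period and then a 1-month interval: 4 weeks + 1 month is roughly two months, assuming writing starts soon after baseline.

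**Step 5. Exposure.** Two trauma scripts of 40 s each: 2 × 40 = 80 s per scan, and 2 × 80 = 160 s for a woman who completes both scans. This describes the exposure; it does not measure risk.

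**Step 6. Do other provisions put a suicide-risk question before the Session 6 scan?** SUDS and POMS are asked before and after each session but scored after it. Section 14 says that part of the psychosocial surveys addresses ideation, and section 8 puts that battery after the scan. None of these supplies a scheduled suicide-risk question beforehand.

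**The case against.** The strongest case on the other side concerns Session 1. The eligibility screen for ideation is the in-house screener, so a count of the MINI and BDI-II alone leaves it out. Section 8 mentions an in-person screening session, and section 29 puts consent at the downtown research centre, whereas Session 1 starts in Coral Gables; both point to consent and screening before Session 1. Section 14 calls the MINI results screening data. The T0 column of Table 1 is empty in every row, including the MMSE, so a T1 mark does not show late use. All of this stands. A reader might infer that women reach the first recall unscreened, or that the MINI follows it. The documents do not support either reading.

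A reader might also infer that a woman with a positive MINI stays in the trial, because the Adverse Event text mentions only support, referral or a hospital plan. That goes too far. Ideation is an exclusion whichever instrument reveals it, and the section 14 steps apply to disclosure through any study instrument. The missing cross-reference is a matter of drafting.

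Other safeguards exist: a check-in by a bilingual trauma therapist, debriefing after recall, contact within 24 to 72 hours of writing, weekly staff contact, and discontinuation by staff. They are real, but they respond to distress or to disclosure; none schedules a suicide-risk question before the Session 6 scan. Section 9 says in general terms that Session 1 questionnaires and interviews are repeated, which could be read to include the MINI. Table 1, the specific schedule, does not mark it at T6, and section 9 gives no order within the session. The suicide risk packet is not reproduced and may set an order; that cannot be checked.

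Finally, a BDI-II given after the scan has value of its own, because it can detect ideation evoked by recall before the woman leaves. That is correct, and it means the item should be added at intake rather than moved there.

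**Conclusion.** The point holds for Session 6, where it follows from the stated order: the BDI-II comes after the scan and the MINI is not scheduled. Followed exactly, the plan repeats scripted recall with neither named suicide-risk instrument scheduled beforehand, and with a MINI result roughly two months old. At Session 1 the BDI-II item also comes after the scan, but the in-house screener probably covers the need.

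The conclusion assumes that the BDI-II is given with the psychosocial battery in which Table 1 and section 10 place it, that the in-house screener is not repeated, and that the unseen packet does not already require a question before the scan. The number of women affected cannot be computed from the documents; at most it is the number who reach the Session 6 scan, out of 36 planned.

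A reader might infer a bias between arms. The documents do not support that: the baseline screen precedes randomisation at the second visit (section 9), and the Session 6 order is the same in every arm.

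**What to change.** Add to section 8, Sessions 1a and 6a (intake): *The BDI-II suicide item is asked and scored at intake, before any trauma script is recorded in Session 1a and before the scan in Session 6a. A positive answer starts the suicide-risk steps of section 14 before any recall. The full BDI-II remains in the post-scan battery.*

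No new instrument is needed. The cost is one item asked twice per session, outside its scale on the first occasion, and about a minute of intake. If recall is withheld at Session 6, that woman's trauma-recall segment is missing, and her post-scan saliva sample no longer follows recall, which affects a secondary outcome. The plan should say how such a case is recorded. The two primary outcomes, the Impact of Event Scale and the Hopkins test, are not measured in that segment.

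Stating where the MINI falls in Session 1, and that a positive result counts toward the existing ideation exclusion, would be an optional clarification. If a risk level such as moderate is used for this, it would be a threshold that the protocol does not now contain.
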